15.2 WARNINGS AND PRECAUTIONS

Clinical trial exclusion criteria must be followed.

16 STATISTICAL PLAN AND DETERMINATION OF SAMPLE SIZE

16.1 DETERMINATION OF SAMPLE SIZE

The sample size is based on the main analysis (t-test) of the primary endpoint that consists of the differences between velusetrag and placebo within each paired treatment cycle (2 per subject).

A total of 16 subject randomized leading to 32 pairs. Accounting for 25% dropouts/missing pairs, 18 pairs should be available for the primary analysis on the subgroup of subjects with history of benefit from , and 24 pairs should be available for the or naïve to analysis on the overall population

With a two-sided significance level of 5%, the planned sample size will lead to power levels above 80% to detect effect size (ES) above 0.7 (see table 16.1 below).

Power for different values of effect size and number of pairs **Table 16.1**

Power for different values of Effect Size* and number of pairs								
Number of pairs ES: 0.6 ES: 0.7 ES: 0.8								
18	67%	80%	89%					
24	80%	91%	96%					
28	86%	94%	98%					
32	91%	97%	99%					

^{*} More than medium to moderate effect size (Cohen, 1988)

Estimates obtained using SAS PROC POWER

If based on a blinded review of the data, the rate of missing pairs is found to be higher the sample size might be increased by the Sponsor.

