7 DISCUSSION OF STUDY DESIGN, INCLUDING THE CHOICE OF CONTROL GROUPS

This study will evaluate the safety, tolerability and efficacy of velusetrag 15 mg once a day versus placebo, in improving the symptoms severity associated with CIPO, in subjects with idiopathic CIPO and CIPO secondary to neurodegenerative conditions (e.g., Parkinsonian Syndromes, etc.).

CIPO is a chronic, rare disease, with fluctuating symptoms and differences in underlying pathology, which may respond differently to active treatment. Therefore, a standard parallel group placebo-controlled study may not allow to detect clear benefit due to the large variability of clinical presentation.

A n=1 cross over, placebo-controlled study design, as the one chosen for the present study, allows to assess the treatment effect in every subject, thereby allowing individual subjects to act as their own control and evidencing a positive effect even in a single subject, avoiding under-estimation of the therapeutic efficacy (Emmanuel, 2012).

Subjects will be evaluated over a total of 16 weeks, receiving either velusetrag 15 mg or placebo, once daily, for four randomized periods of 4 weeks each. The planned treatment time period is considered enough to demonstrate a difference between active treatment and placebo. The washout periods' duration has been selected based on velusetrag and active metabolite half-life.

Efficacy will be assessed after each 4 weeks of treatment for primary analysis. The choice of placebo as comparator will allow for estimation of the real treatment effect of velusetrag and is considered acceptable due to: i) the lack of any approved treatment for CIPO; ii) the fact that symptomatic rescue therapies are allowed, and iii) the close monitoring during a relatively short treatment period. Moreover, participants, that during the study should experience significant exacerbation of CIPO-related gastrointestinal symptoms that are not controlled by permitted medications and are not judged as adverse events, after being reassessed may decide to continue the study and start the subsequent treatment period, or discontinue the study.

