16.3.1 Primary Efficacy Endpoints and Statistical Model of Analysis

The primary endpoint is the change in weekly global gastrointestinal symptoms average index score from pre-treatment to the end of each treatment period.

The average weekly global gastrointestinal symptoms index score is obtained by averaging the scores for each of the 4 symptoms assessed weekly: abdominal pain, bloating, nausea and vomiting. The use of the average of the 4 symptom scores to obtain a global score is similar to the scoring methodology applied for largely used patient questionnaires such as PAGI-SYM (Patient Assessment Gastrointestinal Symptoms) and ANMS-GCSI-DD (American Neurogastroenterology and Motility Society – Gastroparesis Cardinal Symptom Index – Daily Diary).

Rating of symptoms (i.e. abdominal pain, bloating, nausea, vomiting) is using a recall period of 7 days and a Likert scale with the following categories:

- 0 Absent
- 1 Mild (not influencing usual activities)
- 2 Moderate (diverting from, but not urging modification of, usual activities)
- 3 Severe (influencing usual activities markedly enough to urge modifications)
- 4 Extremely severe (precluding daily activities)

The average s	score	ranges	thus	between	0	and 4	- with	lower	scores	representing	a	better	health	for
the subject.														

The primary analysis is performed on the mFAS1.

A stratified t-test will be used to analyze the treatment effect. For the primary analysis on the mFAS1, missing pairs will not be imputed (each subject contributing to at least one pair).

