| Draft Version 1.1 | 20-APR-2023 | 
Section 1.1 is updated to report the decision to not considered the variable stratum in the efficacy analyses and all efficacy sections are updated consequently (i.e., 6.3.1, 6.3.2.1, 6.3.2.2, 6.3.2.4, 6.3.2.8).
 
Section 6.1 is updated to better clarify how subject disposition will be described and to drop tables by stratum.
 
Time from CIPO diagnosis date to informed consent signature described in Section 6.2 is computed in years instead of months.
 
The analysis of primary endpoint on FAS is removed in section 6.3.1.
 
Section 6.3.2.9 related to [REDACTED] is updated including additional details.
 
Section 6.3.2.11 [REDACTED] and section 6.3.2.13 [REDACTED] are updated to consider the variables as
 | Sponsor's review |

| | |
|--|---|
| | Statistical Analysis Plan |
| | 
Sponsor: Alfasigma S.p.A.
 
Protocol: VE-CIP2001/2021
 |

| Status and Version | Release Date | Change Description | Reason/Comment |
|----------------------|--------------|--|------------------|
| | | 
categorical and to include data collected for wash-out/follow-up period and statistical model for [REDACTED]. [REDACTED] are removed.
 
Formal adjustment for section 6.4.3.
 
Further details are included for listings with abnormal values in section 6.4.4 and 6.4.6.
 
[REDACTED] are updated in section 6.4.4.
 | |
| Draft Version 1.2 | 09-MAY-2023 | 
Section 1.1 updated with further details on binary outcome and count data. Fisher exact test was included in the section 6.3.2.2 and 6.3.2.13.
 
ATC codes to identify opioids treatments in section 3.3.3 were updated as well as the ATC code to identify patients who took antibiotics in section 6.3.2.7.
 
Including also start date for prior medications (including the [REDACTED] [REDACTED] start date of medical history condition on which imputation rules for partial dates will be applied to compute the study day.
 
Management of [REDACTED] collected with different unit of measurements where there isn't conversion factor applicable to uniform the unit are described for [REDACTED].
 
Similarly, management of [REDACTED] collected as greater than (>) or lower than (<) will be also described.
 
Mixed models for efficacy parameters considered as continuous variables were updated considering the reference of
 | Sponsor's review |

| | |
|--|---|
| | Statistical Analysis Plan |

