1.1. Changes from The Study Protocol

The endpoints "" reported in section 5.2 SECONDARY STUDY OBJECTIVES AND ENDPOINTS of study protocol are analysed 

The Handling of Missing and Incomplete Data for primary endpoint has been modified in case of pre-treatment value missing. 

The reason for this is to reduce data heterogeneity between subjects 

In addition, missing imputation methodology will be applied only for the primary endpoint of the study while all other secondary endpoints will be based on observed data. For this reason, the rules explained in section 16.3.5 Handling of Missing and Incomplete Data of study protocol for the other endpoints are not reported since not applied.

All efficacy analyses, originally planned to be stratified by randomization stratum, will be performed only overall since all patients were randomized to Stratum 2 , except one that was randomized to Stratum 1 

For the binary outcome (Proportion of subjects with 1-point improvement in ), odds ratio and confidence interval using logistic model will be computed while the Cochran-Mantel-Haenszel test will not be performed due to strata distribution and it will be substituted with Fisher Exact test.

| | |
|--|---|
| | Statistical Analysis Plan |
| | 
Sponsor: Alfasigma S.p.A.
 
Protocol: VE-CIP2001/2021
 |

[figure not shown]
Number of [REDACTED] and number of [REDACTED] will be analyzed as categorical variables and will be separately analyzed for treatment and wash-out/follow-up period. [REDACTED]

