6.3. Efficacy Evaluation

6.3.1. Primary efficacy analysis

Definition of primary endpoint

The primary endpoint is the change in weekly global gastrointestinal symptoms average index score from pre-treatment (Baseline/Reference, depending on the period) to the end of each treatment period.

The weekly global gastrointestinal symptoms average index score is obtained by averaging the scores for each of the 4 symptoms assessed weekly: abdominal pain, bloating, nausea and vomiting.

Each symptom (i.e., abdominal pain, bloating, nausea, vomiting) was rated using a recall period of 7 days and a Likert scale with the following categories:

- 0 – Absent
- 1 - Mild (not influencing usual activities)
- 2 - Moderate (diverting from, but not urging modification of, usual activities)
- 3 - Severe (influencing usual activities markedly enough to urge modifications)
- 4 - Extremely severe (precluding daily activities)

[figure not shown]
[figure not shown]
[figure not shown]

Analysis methodology

| | |
|---|--|
|  | Statistical Analysis Plan |
| | Sponsor: Alfasigma S.p.A. Protocol: VE-CIP2001/2021 |

Considering the evaluable pairs  the  will be summarized 

Of note, each subject should be evaluated twice: once for each cycle. Consequently, each subject can contribute to 0, 1 or 2 pairs and only data that constitute pair evaluable for primary endpoint will be considered in this and in the following analysis.

Differences between velusetrag and placebo will be computed within each cycle 

These analyses will be provided on the mFAS1 without any missing data imputation as primary analysis.

Finally, a listing will be provided on Randomized population considering the intake of each  collected in the eDiary together with the individual gastrointestinal symptoms and the weekly global gastrointestinal symptoms average index score.

Data handling rules

Missing data will be handled as described in [Section 4.4.2](#).

[figure not shown]
Sensitivity analysis

| | |
|---|--|
|  | Statistical Analysis Plan |
| | Sponsor: Alfasigma S.p.A. Protocol: VE-CIP2001/2021 |

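### The power table treats each subject's two cycle differences as independent; if response varies between subjects, a pooled t-test can exceed 5% and a valid subject-level test has less power than printed

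*Protocol*

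**What the plan says.** Protocol 16.1, repeated in SAP 3.5, bases the sample size on a t-test of "differences between velusetrag and placebo within each paired treatment cycle (2 per subject"). Sixteen subjects are counted as 32 pairs. After allowing for 25% dropouts or missing pairs, 18 pairs are expected for the primary analysis (responder/naive subjects) and 24 overall. At a two-sided 5% level the claim is that "the planned sample size will lead to power levels above 80% to detect effect size (ES) above 0.7". The table is indexed by number of pairs only.

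Protocol 16.3.1 names the primary test: "A stratified t-test will be used to analyze the treatment effect". It adds that "missing pairs will not be imputed (each subject contributing to at least one pair"), and mentions no subject term. SAP 6.3.1 notes: "Consequently, each subject can contribute to 0, 1 or 2 pairs". SAP 1.1 drops stratification "since all patients were randomized to Stratum 2", with one exception.

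The primary method in SAP 6.3.1 is largely blacked out. The SAP version history, under Draft Version 1.2, records: "Mixed models for efficacy parameters considered as continuous variables were updated considering the reference of" a model from a published comparison of methods for N-of-1 trials. No visible text in either document gives a within-subject correlation, a between-subject variance of the treatment effect, or a design effect.

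**The concern.** Two velusetrag-minus-placebo differences from one person are independent only if the true treatment effect does not vary between people. Protocol section 7 argues for the multiple n=1 design because patients have "differences in underlying pathology, which may respond differently to active treatment". If so, a subject who does well in cycle 1 will tend to do well in cycle 2, and rho is above 0. A t-test that pools the pairs then has too small a standard error and too many degrees of freedom.

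This is the primary test and the plan's only power statement. If response varies between subjects, either the pooled test fails to hold its 5% or a test that does hold it has less power than the table prints for the same number of pairs. The planned blinded sample-size review responds only to the rate of missing pairs, so it would not reveal this.

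**Working it through.** **Inputs.** From Protocol 16.1 and SAP 3.5: two-sided alpha 0.05; effect size (ES) 0.6, 0.7, 0.8; 18, 24, 28 or 32 pairs; two differences per subject; 25% missing. ES is read as the mean divided by the SD of a single cycle difference, the reading that reproduces the table. Eighteen pairs imply 18 / 0.75 = 24 planned pairs, so 24 / 2 = 12 responder/naive subjects (inferred). The documents give no rho; 0 to 0.5 is assumed.

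**Step 1: reproduce the table.** One-sample t-test, n = pairs, df = n − 1, noncentrality = ES × √n.

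| Pairs | Computed, ES 0.6 / 0.7 / 0.8 | Printed |
|---|---|---|
| 18 | 67.0 / 79.9 / 89.2% | 67 / 80 / 89% |
| 24 | 80.4 / 90.7 / 96.3% | 80 / 91 / 96% |
| 28 | 86.4 / 94.6 / 98.3% | 86 / 94 / 98% |
| 32 | 90.8 / 97.0 / 99.2% | 91 / 97 / 99% |

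All 12 cells agree within 1 point. The arithmetic is right, and it uses independent pairs.

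**Step 2: exact subject-level power with complete subjects.** The mean of two unit-variance differences with correlation rho has variance (1 + rho)/2. With m subjects, noncentrality = ES × √m / √((1 + rho)/2) and df = m − 1. For 18 pairs as 9 subjects with two each, at ES 0.7:

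- rho 0: 0.7 × 3 / 0.707 = 2.97, df 8, power 74.0%. The table's noncentrality is the same (0.7 × √18 = 2.97), so this gap comes only from df 8 in place of 17.
- rho 0.2: power 66.2%.
- rho 0.3: 0.7 × 3 / 0.806 = 2.60, power 62.8%.
- rho 0.5: 0.7 × 3 / 0.866 = 2.42, power 56.8%.

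The ES needed for 80% power is 0.75, 0.83, 0.86 and 0.92 at these four values of rho.

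**Step 3: simulation where some subjects give one pair.** Two exchangeable unit-variance differences per subject, a fixed number of pairs missing at random, 40,000 runs per cell. Pooled test: df = pairs − 1. Subject-mean test: df = subjects with data − 1. The weighted subject-level test uses the same df, with weights from the true rho, so its power is somewhat optimistic. In the table, type I error is at zero mean effect and power is at ES 0.7; the 9-subject powers are the exact values from step 2.

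| Subjects, pairs | Pooled type I error, rho 0.2 to 0.5 | Subject-mean power, rho 0 / 0.2 / 0.3 / 0.5 | Weighted power, same rho | Printed |
|---|---|---|---|---|
| 12, 18 | 6.6 to 9.3% | 72 / 69 / 67 / 64% | 76 / 71 / 69 / 65% | 80% |
| 9, 18 | 7.1 to 11.4% | 74 / 66 / 63 / 57% | same (no single pairs) | 80% |
| 15, 23 | 6.6 to 9.7% | 84 / 81 / 79 / 76% | 87 / 83 / 81 / 77% | no row |
| 16, 24 | not tabulated | 85 / 83 / 81 / 78% | not computed | 91% |

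At rho 0 the pooled type I error was 4.8 to 5.1%. The subject-mean test held 4.8 to 5.1% in every cell. With 12 subjects and 18 pairs the pooled test still rejects in 80% to 77% of trials at ES 0.7, but for rho above 0 that rests on the understated standard error.

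The 15-subject row uses 15 × 2 × 0.75 = 22.5, rounded to 23. It assumes that 16 subjects were randomized and that Stratum 2 in SAP 1.1 is a responder/naive stratum; the label is blacked out.

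**The case against.** **The final test may not be a pooled t-test.** The primary endpoint is continuous, and the version history says models for continuous efficacy parameters follow an N-of-1 reference. The type I error point would fall away if that model carries a subject effect. This stands as a limit: the blacked-out text prevents confirmation. But SAP 3.5 still calls a t-test the main analysis and repeats the table, so the power claim is unsupported either way.

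**The inflation needs a particular null.** If the drug does nothing in anyone, rho is about 0 and the pooled test stays near 5%. Inflation requires a zero mean effect with real individual effects in both directions. Rho of 0.5 is also strong heterogeneity: under a normal model at ES 0.7, Φ(−0.7/√0.5), or about 16% of patients, would be truly harmed. If inference is confined to the patients studied, as the n=1 rationale might suggest, differences between them are not error. These points are fair. However, a power table describes the alternative, where varying response is what section 7 anticipates, and the sample-size text states no such restriction of inference.

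**Part of the gap is the choice of test.** With 12 subjects and 18 pairs at rho 0, simple means already lose about 8 points and the weighted test about 4, through fewer degrees of freedom and, for simple means, unequal weighting. That is correct. Correlation costs a further 5 points for simple means at rho 0.3 (72% to 67%).

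**Enrolment may be kinder than the worst rows.** With 15 subjects and 23 pairs the 80% target is met or missed by about 4 points. With all 32 pairs from 16 subjects, subject-level power at ES 0.7 is 96% at rho 0 and 86% at rho 0.5, against 97% printed. This limits the practical damage but does not make the table correct.

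**Conclusion.** The concern holds and should be fixed. The table is computed correctly, but for independent pairs, an assumption that neither document states and that the design rationale contradicts. At the planned 18 pairs and ES 0.7, subject-mean power is 72% to 64% with about 12 subjects and 74% to 57% with 9, against 80% printed. If the pooled t-test is kept, its type I error is about 7% to 11% across these two layouts for rho of 0.2 to 0.5.

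These figures rest on an assumed rho, exchangeable differences, and pairs missing at random. The power shortfall is firmly established for rho above 0. The type I error point is conditional on two things: that the primary test pools pairs, and that effects vary between subjects around a zero mean.

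**What to change.** Make the subject the unit of the primary test, or confirm in unredacted SAP text that the model already does so. Two options are a one-sample t-test on each subject's mean evaluable cycle difference, or a mixed model on cycle differences with a random subject effect and Kenward-Roger degrees of freedom. Power for that mixed model was not computed here and should be simulated if it is chosen.

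Replace the unqualified claim of more than 80% with power by number of subjects, evaluable pairs and rho. For subject means at ES 0.7 the rows would be about:

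| Subjects, pairs | rho 0 | rho 0.3 | rho 0.5 |
|---|---|---|---|
| 9, 18 | 74% | 63% | 57% |
| 12, 18 | 72% | 67% | 64% |
| 15, 23 | 84% | 79% | 76% |
| 16, 24 | 85% | 81% | 78% |

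The cost is wording in Protocol 16.1 and 16.3.1 and SAP 3.5 and 6.3.1, and a less favourable stated power. No new patients or data are needed. If rho is really 0, the subject-level test gives up about 4 points (weighted) to 8 points (simple means) of power with 12 subjects and 18 pairs.

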16.2 DEFINITION OF STUDY POPULATIONS

Study populations definitions are provided below. The numbers of subjects in each population and reasons for exclusion will the summarized.

All decisions on populations will be taken during the Data Review Meeting and will be detailed in the relevant documents.

16.2.1 Screened Population

The Screened Population is defined as the set of all subjects who provided informed consent.

A screening failure is defined as a subject who has not been randomized to treatment.

16.2.2 Safety Set

The Safety Set (SS) is defined as the set of subjects treated (i.e.: having received at least one of investigational product).

Analysis on the SS will be performed according to the actual treatment received.

16.2.3 Full Analysis Set (FAS)

The Full Analysis Set (FAS) is defined as the set of all subjects randomized and treated.

The Modified-Full Analysis Set 1 (mFAS1) is defined as the set of all subjects responder/naïve to randomized and treated who reported data on the primary endpoint at least once during a velusetrag treatment period and at least once during a placebo treatment period.

Following the intent-to-treat principle analysis on the FAS, mFAS1 will be performed according to the treatment and stratum assigned at randomization.

16.2.4 Per Protocol Set (PPS)

The Per Protocol Set (PPS) is defined as the set of all subjects in the mFAS1 who fulfil the study protocol requirements in terms of compliance to treatment and collection of primary efficacy data and with no major deviations that may affect study results.

Examples of deviations are:

- 1. Intake of study treatment other than the one assigned by the IWRS
- 2. Lack of compliance overall defined by percent compliance (number of number of planned *100) below 80%.

In addition, if within a period, the compliance is below 80%, the primary endpoint data of this period will be excluded from the analysis. E.g., if compliance data are 100%, 100%, 60%, 60%, the subject is included in the PPS (overall compliance at 80%) but the observations of the third and fourth period are excluded.

The complete list of deviations will be defined in a specific protocol deviations handling plan and a blind data review meeting will occur prior to unblinding. The decisions for exclusion of subjects from the PPS will be taken in a blinded manner and documented.

Subjects receiving a study treatment different from the randomized one will be excluded from the PPS. Subjects randomized to a wrong stratification factor level will not be excluded from the PPS and will be analyzed according to the actual stratum (not the randomized one).

16.2.5 Disposition, Demographic and Other Baseline Variables

The number of subjects screened, failed screening (and reason for screening failure), randomized, treated and completing the study treatment periods (and reason for not completing) will be presented in frequency tables by treatment sequence and stratum.

The number of subjects in each analysis population (SS, FAS, mFAS1, and PPS) will be summarized by treatment sequence and stratum.

All major protocol violations will be presented as a frequency table by treatment sequence.

Baseline values are the last recorded values collected prior to treatment initiation.

Subject demographics, medical history and disease characteristics and others baseline characteristics measured before randomization will be summarized descriptively by treatment sequence on the FAS. Selected summaries will be done by treatment sequence and stratification factors (details to be provided prospectively in the SAP).

Selected baseline data will be also summarized on the mFAS1 and PPS.

16.3 STATISTICAL AND ANALYTICAL PLANS

A detailed Statistical Analysis Plan (SAP) analysis plan will be developed and approved prior to unblinding.

Descriptive statistics per sequence, visit/period, and stratum will be presented as number of observations, number of missing observations, mean, standard deviation, median, minimum and maximum and 25th and 75th percentiles for continuous variables; frequency distribution (n, %) for categorical variables.

Graphical visualization for each subject overtime, including all assessments, will be used for the evaluation of efficacy and safety.

All efficacy analyses have the objective to show the superiority of velusetrag over placebo. All statistical analysis will be two-sided at a nominal level of 5%. Confidence intervals will be set at the 95% level.

Analysis of the primary efficacy endpoints will be performed on the mFAS1, FAS and PPS. Results on the mFAS1 will be considered primary. For secondary endpoints, analysis will be performed on selected populations. Details will be provided in the SAP.

Safety analysis based on SS will be presented by actual treatment received in each period.

Most recent version of appropriate coding dictionaries will be used.

SAS software (Version 9.3 or subsequent) will be used for all statistical analyses.

